6.2. Criteria for endpoint evaluation

6.2.1. Primary Endpoint: Safety (DLT), as defined by CTCAE v 5.0.

6.2.1.1. Assessment of Adverse Events: The PI will be responsible for evaluating all AEs at the end of the individual patient study period. CTCAE v 5.0 grade 3 or above will be considered a DLT

6.2.1.2. The reporting procedures to be followed are presented in the "CTEP, NCI Guidelines: Adverse Event Reporting Requirements" which can be downloaded from the CTEP web site ([http://ctep.cancer.gov/protocolDevelopment/electronic\\_applications/docs/aeguidelines.pdf](http://ctep.cancer.gov/protocolDevelopment/electronic_applications/docs/aeguidelines.pdf)).

6.2.1.3. Adverse Laboratory Values

6.2.1.3.1. Not every laboratory abnormality qualifies as an adverse event. A

laboratory test result must be reported as an adverse event if it meets any of the following criteria:

- 6.2.1.3.2. • Is accompanied by clinical symptoms
- 6.2.1.3.3. • Results in a change in study treatment (e.g., dosage modification, treatment interruption, or treatment discontinuation)
- 6.2.1.3.4. • Results in a medical intervention (e.g., potassium supplementation for hypokalemia) or a change in concomitant therapy
- 6.2.1.3.5. • Is clinically significant in the investigator's judgment

6.2.1.3.6. It is the investigator's responsibility to review all laboratory findings. Medical and scientific judgment will be exercised in deciding whether an isolated laboratory abnormality should be classified as an adverse event.

6.2.1.3.7. Any abnormality of safety laboratories ("laboratory panel") will be considered an AE if it is a change from baseline (based on CTCAE v5.0)

6.2.1.4. Adverse Event Characteristics:

6.2.1.5. **CTCAE term (AE description) and grade:** The descriptions and grading scales found in the revised NCI Common Terminology Criteria for Adverse Events (CTCAE) version 5.0 will be utilized for AE reporting.

6.2.1.6. **"Expectedness;"** AEs can be "Unexpected" or "Expected" for expedited reporting purposes only.

6.2.1.7. **Attribution of the AE:**

- Definite – The AE is *clearly related* to the study treatment.
- Probable – The AE is *likely related* to the study treatment.
- Possible – The AE *may be related* to the study treatment.
- Unlikely – The AE is *doubtfully related* to the study treatment.
- Unrelated – The AE is *clearly NOT related* to the study treatment.

6.2.2. **Secondary and Exploratory Endpoints:**

6.2.2.1. Safety profile of intralesional cisplatin as classified by the CTCAE, v5.0

6.2.2.2. Proportion of cisplatin-treated subjects proceeding to surgery without extended local injection-related delay, defined as >30 days from preplanned surgery date (21 days from preplanned surgical date with 7-day window to allow for operating room [OR] scheduling)

6.2.2.3. Time to surgery from intralesional therapy.

6.2.3. **Biomarker and Surrogate Endpoints for Research Purposes:**

6.2.3.1. The below assays will be performed from:

6.2.3.1.1. Blood samples, pre-procedure on the date of the bronchoscopy and pre-procedure on the date of the surgical resection

6.2.3.1.2. Three (3) needle biopsies obtained at the time of bronchoscopy before cisplatin delivery

6.2.3.1.3. Seven (7) needle biopsies obtained from the ex-planted resection specimen (3 for platinated DNA, 1 for tumor organoid, 3 for other biomarker assessments described below)

6.2.3.1.4. Approximately 20 sections of fixed tissue from the resected tumor (final amount to be determined by pathology following obtaining all necessary tissue for clinical care, including any additional candidacy for clinical trials)

Objectives	Endpoints
Secondary To assess pathologic responses (PR) in the resected tumor following a single intra-tumoral administration of cisplatin in subjects with early stage NSCLC	

Proportion of cisplatin-treated subjects with major pathologic response (MPR), i.e., <math>\geq 90\%</math> reduction in viable tumor cells, at the time of NSCLC resection

Proportion of cisplatin-treated subjects with pathologic complete response (pCR), i.e., no residual viable tumor cells, at the time of NSCLC resection

Change from baseline in percent of residual viable tumor cells (% RVT) in cisplatin-treated subjects at the time of NSCLC resection

Exploratory To assess radiologic responses in the tumor following a single intra-tumoral administration of cisplatin in subjects with early stage NSCLC	

Tumor response rate evaluation (<math>\Delta</math> tumor size) according to RECIST 1.1 criteria

To explore the change from pre-treatment baseline in measures of immune activation in the blood and tumor (eg, percentages of immune cell subsets, numbers of T-cell clones, concentrations of serum cytokine levels)	
Pre- and post-treatment in the bronchoscopic biopsy and surgically resected tumor samples, respectively:
 

Tissue levels of immune-related gene expression as measured by appropriate techniques such as RNA-sequencing in biopsy samples collected at diagnosis and time of resection

Tissue frequencies of immune cell subsets determined via semi-quantitative immunohistochemistry (IHC) analysis of diagnostic biopsy and surgically-resected tissue specimens

To assess changes in T cell clonality in blood by TCR-sequencing (via DNAseq) at baseline and after therapy, TCR repertoire sequencing will be performed on the tumor to profile in the blood

Tumor mutational burden will be assessed

Objectives	Endpoints
	
by next generation sequencing.
 
Pre- and post-treatment blood:
 
 
Changes in the concentrations of immune activation and inflammation markers in the serum before and after treatment. Serum cytokine and inflammatory biomarker (e.g., hs-CRP, IL-6, TNF-<math>\alpha</math>) concentrations will be measured by appropriate techniques such as Mesoscale Discovery (MSD).
 
Serum neutrophil-to-lymphocyte ratio (NLR): Defined as neutrophil count divided by lymphocyte count, as determined by complete blood count (CBC) with differential conducted at baseline and after treatment.
 
Change in frequencies of immune cell subsets in blood as measured by flow cytometry (eg, CD3, CD8, PD-1) at baseline and after treatment (absolute frequencies and percent change from baseline).
 
To assess changes in T cell clonality in blood by TCR-sequencing (via DNAseq) at baseline and after therapy. TCR repertoire sequencing will be performed on the biopsy sample of the tumor to ID clones specific to the tumor to profile in the blood.
 

To evaluate cisplatin pharmacokinetic parameters in the blood and to confirm cisplatin exposure and distribution in the	
 
Maximum observed serum concentration (Cmax), area under the concentration-time, half-life (T<math>1/2</math>), clearance of drug after administration (CL), volume of distribution (Vd)
 
 
Cisplatin concentration in the tumor at the site of injection and adjacent tumor regions measured by an ELISA-like method that can detect cisplatinated DNA

### 6.3. Sample Size

6.3.1. The minimum sample size will be 10. Initial dose ranging will be performed in a 3+3 fashion. Additional patients up to a minimum of 10 patients will be enrolled at the recommended Phase II dose to assess for additional AEs.

6.3.2. The maximum sample size, if six patients at each of two dose levels were enrolled, would be 12 patients.

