## 4. **TREATMENT PLAN**

### 4.1. **Agent Administration**

4.1.1. Treatment will be administered intraprocedurally. Reported adverse events and potential risks are described in the Data and Safety Monitoring Plan. No investigational or commercial agents or therapies other than those described below may be concomitantly administered with the intent to treat the patient's malignancy.

4.1.2. The agent will be administered at 3 potential dose levels in a 3+3 design.

4.1.3. IT cisplatin 1mg/ml will be dosed with a delivered volume based on a proportion of the volume of the tumor.

4.1.4. This volumetric dosing approach is being employed to account for the dramatic tumor volume differences seen in this diameter range. Prior studies have most commonly used an empirically derived intratumoral dose of 40mg or less (although have ranged to 100mg intratumorally, Appendix B). To minimize the risk of extravasation of the agent from small tumors we have adopted a volumetric dosing strategy.

4.1.4.1. First dose cohort: The delivered quantity of cisplatin will equal one-fourth (1/4th) of the total tumor volume.

4.1.4.2. De-escalation dose cohort : The delivered quantity of cisplatin will equal one-eight (1/8th) of the total tumor volume This dose cohort will only be used if the 1/4-tumor volume dose cohort is terminated due to DLT.

4.1.4.3. Escalation dose cohort: The delivered quantity of cisplatin will equal one-half (1/2) of the total tumor volume

4.1.4.4. Lower or higher dose cohorts may be pursued if indicated based on the rate of DLT, pending formal review and approval by the appointed Data Safety Monitoring Committee of the UVM Cancer Center. This is a standard approach since the DSMC reviews all AEs and relevant data at any change in dose level (pre-specified or otherwise) before preceding to the next dose level.

4.1.5. Tumor volume will be determined using automated segmentation available in the open-source software platform (<https://chestimagingplatform.org>) and manually verified.

4.1.6. The minimum volume that is feasible to deliver is 0.5mL.

4.1.7. This leads to the following “INITIAL” *example* dosing regimen for tumors of a specified volume, beginning at 1/4th Volumetric Dosing and assuming that < 2 of the first 3 participants have a dose limiting toxicity (DLT), defined as a Grade 3 by the CTCAE v5.0:

Example Tumor Volume(mL)*	Approximate Tumor Diameter (cm)*	INITIAL		First Dose Cohort:	

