		First Dose Cohort: 1/4 Tumor Volume (mL)	Delivered Volume (mL)	IT Cisplatin	Total Cisplatin (mg)
				Not Eligible**	
1.2	1.3	0.3			
1.8	1.5	0.5		0.5	0.5
4.2	2.0	1.1		1.1	1.1
8.2	2.5	2.1		2.1	2.1
14.1	3.0	3.5		3.5	3.5
22.5	3.5	5.6		5.6	5.6
33.5	4.0	8.4		8.4	8.4
47.7	4.5	11.9		11.9	11.9
65.5	5.0	16.4		16.4	16.4

\*Calculated based on volume of a sphere  
\*\*Minimum delivery volume is 0.5mL

4.1.8. The following are *example* doses for the DE-ESCALATION cohort:

Example Tumor Volume(mL)*	Approximate Tumor Diameter (cm)*	DE-ESCALATION		 Second Dose Cohort: IT Cisplatin Delivered Volume (mL)	Total Cisplatin (mg)	
		Second Dose Cohort: 1/8 Tumor Volume(mL)	Delivered Volume (mL)			
			Not Eligible**			
1.2	1.3	0.2				
1.8	1.5	0.2		Not Eligible**		
4.2	2.0	0.5		0.5	0.5	
8.2	2.5	1.0		1.0	1.0	
14.1	3.0	1.8		1.8	1.8	
22.5	3.5	2.8		2.8	2.8	
33.5	4.0	4.2		4.2	4.2	
47.7	4.5	6.0		6.0	6.0	
65.5	5.0	8.2		8.2	8.2	

\*Calculated based on volume of a sphere  
\*\*Minimum delivery volume is 0.5mL

4.1.9. The following are *example* doses for the ESCALATION cohort:

Example Tumor Volume(mL)*	Approximate Tumor Diameter (cm)*	ESCALATION			Second Dose Cohort Total Cisplatin (mg)
		Second Dose Cohort: 1/2 Tumor Volume(mL)	Second Dose Cohort	Total Cisplatin (mg)	
1.2	1.3	0.6	0.6	0.6	0.6
1.8	1.5	0.9	0.9	0.9	0.9
4.2	2.0	2.1	2.1	2.1	2.1
8.2	2.5	4.1	4.1	4.1	4.1
14.1	3.0	7.1	7.05	7.05	
22.5	3.5	11.3	11.3	11.3	
33.5	4.0	16.8	16.8	16.8	
47.7	4.5	23.9	23.9	23.9	
65.5	5.0	32.8	32.8	32.8	

\*Calculated based on volume of a sphere

\*\*Minimum delivery volume is 0.5mL

4.1.10. Dose escalation will be performed as follows:

Number of Patients with DLT at a Given Dose Level	Escalation Decision Rule
0 out of 3	Enter 3 patients at the next escalation dose.
$\geq 2$	Dose escalation will be stopped. This dose level will be declared the maximally administered dose (highest dose administered). Three (3) additional patients will be entered at the next lowest dose level if only 3 patients were treated previously at that dose. If this is the first dose evaluated, a lower dose level will be established, in concert with DSMC, and 3 patients enrolled to that level.

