1 out of 3	
Enter at least 3 more patients at this dose level.
 
 
If 0 of these 3 patients experience DLT, proceed to the next dose level.
 
If 1 or more of this group suffer DLT, then dose escalation is stopped, and this dose is declared the maximally administered dose. Three (3) additional patients will be entered at the next lowest dose level if only 3 patients were treated previously at that dose.
 

$\leq 1$ out of 6 at highest dose level below the maximally administered dose	This will be the recommended phase 2 dose. At least 6 patients must be entered at the recommended phase 2 dose.

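### The stated maximum of 12 patients does not follow from the plan's own rules, which need 13 to 22 with ten at the recommended dose and up to 18 without that expansion

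*Combined protocol and SAP*

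**What the plan says.** Section 6.3.2 gives the upper bound: "The maximum sample size, if six patients at each of two dose levels were enrolled, would be 12 patients". Section 6.3.1 opens with "The minimum sample size will be 10" and goes on: "Additional patients up to a minimum of 10 patients will be enrolled at the recommended Phase II dose to assess for additional AEs".

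Section 4.1.2 sets the number of levels: "The agent will be administered at 3 potential dose levels in a 3+3 design". Dosing starts at the middle level, 1/4 of tumor volume (4.1.4.1). The upper level is 1/2 (4.1.4.3) and the lower is 1/8 (4.1.4.2), of which the protocol says: "This dose cohort will only be used if the 1/4-tumor volume dose cohort is terminated due to DLT".

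The table in 4.1.10 allows three or six patients per level and refills the next lower level to six once escalation stops. It also requires: "At least 6 patients must be entered at the recommended phase 2 dose". Section 4.1.4.4 lets the DSMC approve further levels, and 6.4.1 says that the escalation scheme alone determines the sample size.

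**The concern.** A stated maximum should cover every path that the escalation rules permit. The figure of 12 counts two levels where the protocol has three, and six patients at the recommended dose where the preceding paragraph calls for more. Because 6.4.1 gives no other basis for the size of the trial, a maximum that does not follow from the escalation rules has no justification.

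If 12 is treated as binding, the team may reach it before the expansion is complete, or before a de-escalation cohort is finished. It must then leave its own rule unfulfilled or enrol beyond the stated size. If the expansion is what gives way, the recommended dose rests on six patients instead of ten.

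**Working it through.** **Inputs**
- Three levels: 1/8, 1/4 (start) and 1/2 (4.1.2, 4.1.4).
- Cohorts of three. 0 of 3 with DLT: escalate. 1 of 3: three more at the same level. Two or more: stop (4.1.10).
- After stopping, three more at the next lower level if it has only three. If 1/4 ends for DLT, 1/8 opens (4.1.10, 4.1.4.2).
- At least six at the recommended dose (4.1.10).
- Expansion to ten (6.3.1), read either as (A) ten at the recommended dose or (B) ten in the whole trial.

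**The plan's own figure.** 6 patients × 2 levels = 12. It reproduces under its own condition, with no expansion and no third level.

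**How many levels are used.** The start is the middle level. From there the rules go up to 1/2 or down to 1/8 before a recommended dose can be declared, so every path to one treats at least two levels.

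**Totals for trials that find a recommended dose** (all paths enumerated, full cohorts of three)

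| | No expansion | (A) ten at recommended dose | (B) trial total at least ten |
|---|---|---|---|
| Two levels, 3 at the other level | 3 + 6 = 9 | 3 + 10 = 13 | 10 |
| Two levels, 6 at the other level | 6 + 6 = 12 | 6 + 10 = 16 | 12 |
| Three levels, 6 and 3 at the others | 6 + 3 + 6 = 15 | 6 + 3 + 10 = 19 | 15 |
| Three levels, 6 and 6 at the others | 6 + 6 + 6 = 18 | 6 + 6 + 10 = 22 | 18 |

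**A path that reaches 18 without expansion**
1. 1/4: 0 of 3 with DLT. Escalate (3 treated).
2. 1/2: 1 of 3, then at least one DLT in the next three. Stop (6 more, 9 in all).
3. Back to 1/4: three more patients, bringing that level to at least 2 DLTs in 6 (12 in all).
4. 1/8 opens and takes six (18 in all).

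**How often the total exceeds 12.** The documents give no DLT rates, so the rates below are assumptions, in the order 1/8, 1/4, 1/2. Each cohort result has binomial probability C(3,k) p^k (1−p)^(3−k). Path probabilities are products of these, summed over the paths with a total above 12.

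| Assumed DLT rates | (A) P(N > 12) | (A) expected N | (B) P(N > 12) |
|---|---|---|---|
| 5/10/10% | 99.7% | 13.9 | 0.2% |
| 10/20/33% | 96.6% | 14.6 | 3.4% |
| 30/30/30% | 70% | 13.2 | 4.0% |

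Under (A), every trial that stays at or below 12 in this enumeration found no tolerable dose and ended with 6, 9 or 12 patients. One further exception arises if enrolment at 1/4 stops as soon as the first two patients both have DLTs: 2 + 10 = 12.

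**Precision if the expansion is dropped.** With zero DLTs in n patients, the one-sided 95% upper limit is 1 − 0.05^(1/n). For n = 6 it is 39%. For n = 10 it is 26%.

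**The case against.** The strongest counter-argument is that ten means the trial total. Section 6.3.1 itself gives a minimum sample size of ten. If ten were required at the recommended dose, that minimum would also be wrong, since a trial that finds a dose would ordinarily need 13. On the trial-total reading two levels give 10 to 12 patients, and 6.3.1 and 6.3.2 agree. Section 6.3.2 is also conditional on two levels, and the example-dose tables label both the 1/8 and the 1/2 cohort as the second, which suggests the authors pictured the starting level plus one other.

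Part of this stands. The reading is genuinely open, and on the second reading an excess over 12 is rare: the 18-patient path has probability 0.2% and 2.0% at the first two sets of rates above. The figure of 22 is about as rare on the first reading (0.2% and 1.8%). Opening 1/8 after an escalation and a return to 1/4 also relies on 4.1.4.2, because 4.1.10 does not spell that step out. Finally, no rule in the protocol halts enrolment at 12, so the consequences described depend on how the figure is used.

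None of this makes 12 the maximum. The literal wording of 6.3.1 places the additional patients at the recommended dose. On the other reading, the three-level path is still permitted.

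**Conclusion.** The concern holds. Twelve is correct only for six patients at each of two levels with no expansion, and it is not the maximum under either reading of 6.3.1.

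- **Ten at the recommended dose:** 13 or 16 patients over two levels, up to 22 over three. The stated maximum is exceeded in almost every trial that finds a recommended dose.
- **Ten in total:** 12 is right for two levels, but the rules allow 18 over three. The excess is possible but unlikely, at most a few percent.

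The counts rest on full cohorts of three and on the three named levels. The probabilities rest on assumed DLT rates. Even 22 and 18 are not hard caps, because 4.1.10 asks for at least three more patients after 1 of 3, and 4.1.4.4 allows further levels. The dose-finding rule and the descriptive primary analysis are unaffected. The stated sample size is wrong and must be corrected.

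**What to change.** Rewrite 6.3 so that 6.3.1, 6.3.2 and 4.1.10 agree:
1. State whether ten is the number at the recommended dose or the trial total.
2. Give the matching maximum: 16 for two levels and 22 for three if at the recommended dose; 12 and 18 if the trial total.
3. If ten is at the recommended dose, correct the stated minimum as well. A trial in full cohorts that finds a dose needs at least 13, and one that finds none can end with fewer.
4. Say that any level added under 4.1.4.4 raises the maximum.
5. Carry the figure into the accrual statement (6.3.3) and the approvals.

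The cost is a restatement of the numbers in one section. No escalation rule changes.

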6.3.3. Accrual would be anticipated to occur over a one year time period

6.4. Power:

6.4.1. Primary endpoint: The sample size in this study is determined by the dose escalation protocol and is thus not driven by considerations of statistical power for between group comparisons.

6.5. Statistical Analysis Plan

6.5.1. Primary Endpoint: Statistical analysis will consist of descriptive summaries of the treated patients along with a summary of the dose-escalation sequence and determination of the MTD. Adverse events, including type and grade, will be tabulated according to dose tier.

7. DATA SAFETY AND MONITORING

7.1. Trial Safety: Identification of risks and plans to minimize risk

Expected Risks	Frequency

Renal injury/failure (reported with systemic administration, never reported with intratumoral delivery)

	 Occurs frequently  Occurs infrequently  Occurs rarely  Frequency unknown

Myelosuppression (reported with systemic administration, never reported with intratumoral delivery)

	 Occurs frequently  Occurs infrequently  Occurs rarely  Frequency unknown

Neurologic side effects, including hearing impairment (reported with systemic administration, never reported with intratumoral delivery)

	 Occurs frequently  Occurs infrequently  Occurs rarely  Frequency unknown

Hepatic injury (reported with systemic administration, never reported with intratumoral delivery)

	 Occurs frequently  Occurs infrequently  Occurs rarely  Frequency unknown

Nausea/vomiting (known but rare adverse event with intratumoral cisplatin)

	 Occurs frequently  Occurs infrequently  Occurs rarely  Frequency unknown

Significant bleeding (defined as >100mL is rarely reported with peripheral biopsies

	 Occurs frequently  Occurs infrequently

<1.0%). Unknown if risk increases with additional research biopsies.
	 Occurs rarely  Frequency unknown

 
Lung or airway injury including pneumothorax. Pneumothorax is reported with peripheral biopsies. Unknown if this risk increases above that associated with performing clinically indicated biopsies since the lesion and needle location will be already established. Other risks to the airway or lung are possible (e.g. pneumonitis) but are not reported or expected.
 
	 Occurs frequently  Occurs infrequently  Occurs rarely  Frequency unknown

Other potential risks:

1. Incorrect ROSE diagnosis is very rare, but could lead to cisplatin delivery into a lesion other than a NSCLC. Further, a single, resectable lesion from a metastatic site is also an unusual presentation. Presentation of small cell lung cancer with a single peripheral nodule is also unusual. Although cisplatin is active against both small cell lung cancer, and the most common metastatic lesions (bladder, colorectal, breast, prostate, and head and neck), injection into a tumor other than a NSCLC would be considered an adverse event and reported to the IRB. Similarly, in the extremely rare circumstance that there would be an injection into a lesion with a ROSE diagnosis of NSCLC, but a final diagnosis of a benign disease, this would also be considered an adverse event and reported to the IRB.
2. Delay in surgical resection. Although not clearly documented in the setting of systemic neoadjuvant IV therapy for Stage I or II NSCLC this is possible. However, known adverse events related to a single dose of cisplatin would be anticipated to resolve within 30 days making this unlikely. This would also be considered an adverse event and reported to the IRB.

7.1.1. Planned safety tests/procedures/observations to be performed as measures to protect participants against foreseeable risks.

7.1.1.1. Pre-procedure evaluation by Cardiothoracic Surgery to insure resectability.

7.1.1.2. Follow up phone call, video, or face-to-face visit performed by a physician, advanced practice practitioner (APP), or nurse the day after the bronchoscopy

7.1.1.3. Evaluation (video/telephone or face-to-face) by a physician or APP, 5-9 days post-bronchoscopy

